Specific Aim 3: To investigate the influence of VRC01LS and 10-1074 treatment on the magnitude and quality of antiviral innate and adaptive immune responses. Data from clinical trials in HIV-1-infected adults show that bNAbs can profoundly influence autologous HIV-1 immune responses. We will use comprehensive phenotypic and functional assays to profile effects of bNAb treatment on biomarkers of immune activation and on innate cellular immune responses, coupled with RNA-Seq-based gene expression studies in selected immune cell subsets. In addition, the evolution of neutralizing antibody breadth and the frequency and functionality of HIV-1-specific T cells will be analyzed, and combined with viral sequencing data (generated in Specific Aim 2) to identify viral immune escape.

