5.5. Recruitment Process

Children who enrolled in the EIT study and have reached at least 96 weeks of life and meet entry criteria are eligible for the intervention (and 4 additional children outside of the EIT Study may be eligible for the PK Step only). All children enrolled in the EIT Study will be eligible for screening for the proposed intervention after 84 weeks of ART (and may enter the intervention at or after 96 weeks of ART). Screening evaluation and testing will be performed as part of the routine visits in the EIT Study. By definition, all participants in the EIT Study meet certain baseline criteria to be part of the EIT Study. For *in utero* infected children, this includes being HIV DNA PCR positive within 96 hours of life and starting ART before 7 days of life. For intrapartum infected children, it includes being HIV DNA PCR negative by 96 hours of life, but HIV positive and on ART before 57 days of life.

To allow for careful monitoring of participant safety, no more than two children will enroll per week for the entire study (regardless of site of enrollment). We anticipate that mothers/caregivers for almost all eligible children (90-100%) will choose to have their children participate in the intervention study. We anticipate this high acceptability based on their current engagement in the EIT study, the potential future benefits to HIV-infected children if the intervention is effective, and the interest expressed by mothers/caregivers in potential alternatives to daily ART dosing. We therefore anticipate a sample size of 20-36 EIT children for the intervention study (if 35-40 children are available at or after 96 weeks from EIT, 0-5 mothers/caregivers decline, and 4-10 are ineligible). An additional 4 non-EIT children may participate in the PK Step in the event that fewer than 12 EIT children are immediately available for this study step at the time it is enrolling (i.e., if fewer than 12 EIT children have reached the 96 week eligibility window at the time the PK Step is enrolling, or if a greater number than anticipated are ineligible or do not consent). Thus, the total possible number of participants in all study steps is 36 if all PK Step participants are from EIT, but may be as high as 40 if 4 non-EIT participants are enrolled in the PK Step.

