Step 1 Week 8-32 Visits (if remaining in Step 1)

- Perform physical exam
- Adherence Assessment
- Acceptability Assessment (at Week 8)
- Continue ART while remaining in Step 1
- VRC01LS and 10-1074 given at Weeks 8, 12, 16, 20, 24, 28, 32
- Samples obtained for: HIV-1 RNA monthly (at Weeks 8, 12, 16, 20, 24, 28, 32); hematology, CD4/CD8, and LFTs (at Weeks 10, 14, 18, 22, 26, and 30); stored PBMC/plasma monthly (at Weeks 8, 12, 16, 20, 24, 28, and 32), qualitative HIV DNA PCR monthly (at Weeks 8, 12, 16, 20, 24, 28, and 32), whole genome sequencing (Week 8), quantitative HIV DNA PCR from stored PBMC every 8 weeks (at Weeks 8, 16, 24, and 32), immune profiling (at Weeks 8, 16, 20 (optional), 24, and 32), ELISA (at Weeks 8, 16, 24, and 32), PK testing (at Weeks 8, 12, 16, 20, 24, 28, and 32).

Step 2 Week 0 (must coincide with a Step 1 Week 8, 12, 16, 20, 24, 28, or 32 Visit)

- Perform physical exam
- Discontinue ART
- Adherence Assessment
- Acceptability Assessment
- VRC01LS and 10-1074 given
- Samples obtained for: HIV-1 RNA, CD4/CD8, stored plasma/PBMC, qualitative DNA PCR, whole genome sequencing, quantitative HIV DNA PCR from stored PBMC, immune profiling, ELISA and PK testing

Step 2 Non-infusion Visits (Weeks 1, 2, 3, 6, 10, 14, 18, 22)

- Perform physical exam (all visits)
- Samples obtained for: HIV-1 RNA (all visits), hematology (at Weeks 6, 10, 14, 18, and 22), CD4/CD8 (at Weeks 6, 10, 14, 18, and 22), LFTs (at Weeks 1, 6, 10, 14, 18, and 22), stored plasma/PBMC (only at non-infusion visits at Weeks 2 and 6), qualitative DNA PCR (all visits), immune profiling (optional at Week 2)

Step 2 Infusion Visits (Weeks 4, 8, 12, 16, 20)

- Perform physical exam (all visits)
- Acceptability Assessment (Week 12)
- VRC01LS and 10-1074 given
- Samples obtained for: HIV-1 RNA (all visits), stored plasma/PBMC (all visits), qualitative DNA PCR (all visits), quantitative HIV DNA PCR from stored PBMC (at Weeks 4, 8, 16), immune profiling (at Weeks 4, and 16, optional at Weeks 12 and 20), ELISA (at Weeks 4, 8, 16), PK testing (at Weeks 4, 8, 12, 16, 20)

Step 2 Week 24 Visit (or last visit off ART)

- Perform physical exam
- Acceptability Assessment
- VRC01LS and 10-1074 given (if visit at 24 weeks, but not if last Step 2 visit for rebound)
- Samples obtained for: HIV-1 RNA, CD4/CD8, stored plasma/PBMC, qualitative DNA PCR, whole genome sequencing, quantitative HIV DNA PCR from stored PBMC, immune profiling, ELISA, PK testing

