10.1.2. Proportion Remaining Virally Suppressed: The next objective of Aim 1 is to evaluate the proportion of children in whom HIV RNA remains <400 copies/mL after 32 weeks of dual bNAb treatment (24 weeks off ART). With a sample size of 20 children (the minimum number expected), safety and PK evaluations will be descriptive, and there will be reasonable precision to estimate the proportion with HIV viral suppression. For example, if the observed proportion with HIV RNA <400 copies/mL is 70%, then this includes 46% to 88% with 95% confidence (based on exact confidence limits) and so there would be evidence that HIV RNA can be maintained suppressed in 46% or more of children. If the observed proportion is lower than 70%, this study will have value as proof-of-concept but is less likely to be of importance as an alternative treatment to ART. Based on data from the CHER Study [52] and from a randomized treatment interruption trial in Kenya [58], <6% of children treated in the first year of life are expected to remain virally suppressed by 6 months off ART. Thus, we believe that demonstrating at least 30% success at 6 months is of scientific interest for this proof-of-concept trial. If the observed proportion is 30% suppressed with an N=20, then a 95% confidence interval will be from 12% to 54% (based on exact confidence limits), and would indicate a biologic effect of the intervention. Thus, for an observed proportion of 30%, we will reasonably be able to rule out low true proportions (e.g. <12%) or high proportions (e.g. >54) and conclude that this strategy achieves suppression in a subset of individuals (even if it is not be useful for most treatment purposes). Accordingly, we have based study stopping criteria on the probability of achieving 30% success (see Section 13.8.1). This approach provides a balance between maximizing the scientific benefits of the study, while not allowing an excessive number of participants to experience viral rebound in the event that there is little treatment benefit from the dual bNAb strategy.

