10.3.5. Associations between immune parameters and clinical/virological characteristics: Correlations will be calculated between biomarkers of HIV reservoir size (total HIV DNA, genome-intact HIV DNA, plasma RNA) and (i) proportions of individual leukocyte and CD4 memory T cell subsets, (ii) phenotypic markers of T, B, NK cell and dendritic/monocyte cell markers, (iii) proportions and functions of HIV-specific CD4 and CD8 T cells, NK cells, and neutralizing antibody breadth and (iv) gene expression patterns in specific immune cell subsets. Correlations will be cross-sectionally determined at pre-bNAb infusions and at selected timepoints during the subsequent study, using Spearman correlations. In addition, correlations between immunological and virological parameters across multiple timepoints will also be calculated, using generalized estimated equations for repeated measures (GEEs). Associations between changes of specific HIV-1 reservoir biomarkers during given time intervals and corresponding changes in immunologic measures will also be analyzed. In addition, possible associations between immune responses and viral rebound kinetics after antiretroviral treatment interruption will also be explored.

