**Figure 1: Study Schematic**

## 2.2 Study Objective Addressed in this SAP

This SAP addresses the following primary objective listed in the study protocol for Specific Aim 1 (other than the PK component of the objective for the PK Step and Step 1a which has been addressed previously), which includes the major outcomes for evaluating the effect of the study treatment. Other study objectives in the protocol will be addressed separately.

Analysis of the study objectives below will be analyzed under a proof-of-concept framework. This study does not have a control arm; however, 95% confidence intervals will be reported.

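### Protocol 10.3.5 plans GEE associations in about 20–36 children and specifies no small-sample correction; with default sandwich inference, nominal 5% tests would run at about 6–19% under assumed inputs

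*Protocol*

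**What the plan says.** Protocol 10.3.5 describes how immune measures will be related to reservoir and virological measures. At single timepoints this is done "using Spearman correlations". For repeated measures, "correlations between immunological and virological parameters across multiple timepoints will also be calculated, using generalized estimated equations for repeated measures (GEEs". Nothing further is given: no link, working correlation, variance estimator, reference distribution, significance level or confidence level.

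The number of clusters comes from two places. Protocol 5.5 states: "We therefore anticipate a sample size of 20-36 EIT children for the intervention study". Protocol 10.1.2 works from the low end: "With a sample size of 20 children (the minimum number expected".

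The analysis serves Specific Aim 3, which Protocol section 3 lists among the primary objectives: "To investigate the influence of VRC01LS and 10-1074 treatment on the magnitude and quality of antiviral innate and adaptive immune responses". Protocol 10.1.2 adds that Aim 2 and Aim 3 data, including associations between immune responses and viral control, are meant to strengthen the reading of the uncontrolled efficacy result.

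The SAP covers Specific Aim 1 only. Its section 2.2 leaves other objectives to separate documents, and GEE is not mentioned. Its interval statement, "This study does not have a control arm; however, 95% confidence intervals will be reported", concerns the Aim 1 objective.

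**The concern.** The usual GEE standard error is the sandwich estimator, referred to a normal distribution. It is valid as the number of independent clusters grows. With few clusters it fails in two ways: the fitted residuals are too small, so the variance is biased downward, and the normal critical value ignores the variability of the variance estimate itself. Both make intervals too short and p-values too small. The number that matters is the count of children, not of samples, so repeated visits do not help.

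The rest of the plan mostly uses methods suited to small samples: exact binomial limits, Fisher's exact and Wilcoxon tests, Spearman correlations and an empirical-Bayes t-test. The GEE is the large-sample method left unqualified. At stake are false immune–virological associations being offered as support for a treatment effect in a trial with no control group.

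**Working it through.** The plan states no error rate, power or level for the GEE, so there is no figure of its own to reproduce on this point. (The exact limits in Protocol 10.1.2 do reproduce: 14/20 gives 45.7%–88.1% and 6/20 gives 11.9%–54.3%.)

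**Inputs from the documents**
- Clusters: K = 20 to 36 children (Protocol 5.5 and 10.1.2).
- Visits: m = 5 per child. Protocol 7.7.1 has non-optional immune profiling at Step 2 Week 0, Weeks 4 and 16 ("immune profiling (at Weeks 4, and 16, optional at Weeks 12 and 20"), Step 2 Week 24 and Step 3 Week 24.

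**Assumed inputs, because the documents give none**
- Two-sided 5% level and identity link.
- Independence or exchangeable working correlation.
- Outcome ICC 0.5 or 0.8; marker ICC from 0 to 1.
- Normal or untransformed log-normal marker; 0 or 2 extra covariates.
- True association zero.

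**Estimators compared** (3,000 simulated trials per setting)
- Default: V = A⁻¹ [Σ XᵢᵀWᵢ rᵢrᵢᵀ WᵢXᵢ] A⁻¹, where A = Σ XᵢᵀWᵢXᵢ. Reject if |b|/SE > 1.96.
- Mancl-DeRouen: replace rᵢ by (I − Hᵢᵢ)⁻¹rᵢ, where Hᵢᵢ is child i's leverage block. Refer to t on K − p degrees of freedom.

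Simulation standard error: √(0.05 × 0.95 / 3000) = 0.4 points at 5%, and √(0.19 × 0.81 / 3000) = 0.7 points at 19%.

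**Selected results** (exchangeable working correlation, outcome ICC 0.5, one marker, no extra covariates except where stated)

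| Marker | K | Default error | Mancl-DeRouen + t | Typical width ratio |
|---|---|---|---|---|
| Normal, ICC 0.5, 2 covariates | 20 | 9.0% | 4.3% | 1.20 |
| Same | 36 | 7.6% | 4.9% | 1.10 |
| Normal, child-level (ICC 1) | 20 | 11.3% | 5.5% | 1.28 |
| Same | 36 | 8.2% | 5.2% | 1.15 |
| Log-normal, ICC 0.5 | 20 | 14.7% | 6.6% | 1.31 |
| Same | 36 | 11.9% | 7.0% | 1.18 |
| Log-normal, child-level | 20 | 18.2% | 6.0% | 1.46 |
| Same | 36 | 15.5% | 5.9% | 1.29 |

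**All settings, default inference**
- 20 children: 7.7%–19.0%. 28 children: 6.5%–17.4%. 36 children: 6.8%–16.5%.
- Roughly symmetric markers, 20–36 children: 6.5%–12.8%. Untransformed log-normal markers: 11.4%–19.0%.
- A further run at outcome ICC 0.6 gave 6%–19%, so I state the range as about 6–19%.
- If only 10–15 children gave usable samples: 8.8%–25.5%.

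**All settings, corrected inference, 20–36 children**
- Mancl-DeRouen with t: 3.7%–7.4%.
- Kauermann-Carroll with t: 4.6%–11.3%. The high values are for skewed markers.

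**Interval width.** The corrected interval is typically 1.08 to 1.46 times the default one, so the default is narrower by 1 − 1/1.08 = 7% to 1 − 1/1.46 = 32%. The t reference explains only part of this. With p = 2, t(18)/1.96 = 2.101/1.96 = 1.07 at 20 children, and t(34)/1.96 = 2.032/1.96 = 1.04 at 36. The rest is the variance correction. With an extreme untransformed value, a single analysis can widen more than these typical ratios.

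**The case against.** The strongest reply is that silence is not a method choice. Section 10.3.5 is a short outline. It does not specify a sandwich variance with a normal reference, and it sets no 5% level. The SAP defers Aim 3 to a separate document, where estimator detail would normally sit and which is not available here. That stands, and it is why the error rate can only be stated conditionally.

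A reader might infer that the plan's own 5% error rate is really some fixed higher figure. The documents do not support this. Within-child correlation, marker distribution and adjustment covariates are not given, and the upper half of the range needs skewed, untransformed or child-level markers. Nor is the inflation generally two to three times nominal: the low end is 6.5/5 = 1.3 times.

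A reader might also infer that a primary result is compromised, because Aim 3 appears under the primary objectives. It is not. The primary endpoints are adverse events and viral suppression under Aim 1, and the stopping rules in Protocol 13.8.1 use no GEE. For suppression and time to rebound, Protocol 10.1.3 names binary regression and rank correlations. Testing many marker pairs is a separate multiplicity question, which a variance correction does not answer.

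What remains is that, in the documents supplied, 10.3.5 is the only specification of this analysis, and the method it names is anti-conservative at this size when run in its usual form.

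**Conclusion.** The point holds conditionally. GEE is planned for immune–virological associations in about 20–36 children with no small-sample correction specified. If the uncorrected sandwich with a normal reference is used, nominal two-sided 5% tests would run at about 6–19%, or about 6–13% for roughly symmetric markers. Intervals would typically be about 7–32% too narrow relative to the corrected ones. This assumes 5 visits per child, outcome ICC 0.5–0.8 and symmetric to log-normal markers.

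The skewed end is plausible. Protocol 10.2.1 expresses reservoir results as copies per mL or per million cells, and 10.3.5 mentions no transformation. The documents do not establish that end, however. The simulations contained no non-detects, so neither the inflation nor the repair has been shown for heavily censored markers.

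Severity is low: this is a cheap improvement to supporting Aim 3 analyses.

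**What to change.** Add to Protocol 10.3.5, or to the separate Aim 3 analysis plan:

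- GEE standard errors will use the Mancl-DeRouen bias-corrected sandwich variance. Tests and intervals will use a t reference with degrees of freedom equal to the number of contributing children minus the number of regression parameters. The working correlation will be named.
- Right-skewed assay values will be log-transformed before modelling.
- The handling of non-detects will be stated. Protocol 2.1.4 reports HIV DNA below the detection limit in most of the first children treated in the first week of life, and a log transformation alone does not settle those values. Protocol 10.2.1 already plans Tobit regression for censored HIV-1 DNA changes, so the two sections should be consistent.

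Kauermann-Carroll should not be offered as an equivalent, because it left up to 11.3% error with skewed markers.

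The cost is a software option and some drafting, with no new data and no design change. The downside is that intervals become about 1.1–1.5 times as wide, so fewer associations will reach nominal significance.

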11. DATA HANDLING AND RECORD KEEPING

11.1. Data Management Responsibilities

Data will be entered by clinical study staff onto standardized case report forms (either paper or electronic) at the sites. Electronic data capture will occur using Medidata Rave, supported by Frontier

Science (please see Human Subjects Protections Section 13 for a description of data storage and access plans, and security of the data). A data manager will incorporate basic error checking capability to minimize data entry errors and to allow rapid querying of the sites for illogical or missing data. The data manager will generate monthly accrual reports as well as periodic reports (approximately 3-monthly) that will summarize basic demographic data and reported aggregate diagnoses, to allow real-time review of enrollment/data.

11.2. Source Documents

The following data items will be considered source documents:

- **Signed Consent Form**
- **Certified Copies of Clinical records:** photocopies of clinical records, including hospitalization notes (where necessary) will be made at every visit and all copies will be certified as true copies of the original by the person making the photocopy. This will be documented by signing and dating a "certification of copy" stamp on the photocopy and those copies will be filed in the study participant's file at the site.
- For any death of a study participant while on study.
 - Copies of death certificate when available.
 - Copies of hospital inpatient or outpatient/clinic records with information thought by the Study Physician to be directly related to the participant's death.
 - Copy of the completed verbal autopsy form.
 - Any laboratory or other clinical investigation/procedure report containing information directly related to the participant's death.

11.3. Quality Control and Assurance

1. The study physician will review all completed CRFs.
2. Study nurses and study physician will be responsible for the following:
 - a. Weekly internal audits of participants' files
 - b. Create checklist and follow-up logs
3. Administrative assistants are responsible for:
 - a. Updating follow-up logs and appointment book
 - b. Confirming the availability of checklist in the files. The checklist should include:
 - i. Locator form filled and signed
 - ii. Enrolment consent signed with time and date of consent
 - iii. Laboratory information
 - iv. Pharmacy information

Keyed data will be reviewed by a second person (either a study physician or study nurse) whenever feasible, to improve quality control.

If an error, inconsistency or incomplete data is identified, the CRF will be tagged "unverified" until the error is resolved. If the original staff member is not available to make corrections, the study physician or other research nurse will make corrections or completions on his/her behalf provided they have access to the correct information.

There are additional levels of quality control, which will occur at the Data Manager level (Frontier Science). Error checking is part of the RAVE data entry program and assists the keyer in identifying problems. The keyer is notified by the program feature of a logic check function that gives a detailed

explanation of the incomplete or inconsistent data. This allows for potential errors to be resolved prior to CRF completion.

12. CLINICAL SITE MONITORING

Site monitors under contract to the National Institute of Allergy and Infectious Diseases (NIAID) will visit participating clinical research sites to review participants records, including consent forms, CRFs, medical records (e.g., physicians' progress notes, nurses' notes, individual's hospital charts), and laboratory records to ensure protection of study participants, compliance with the EC/IRB approved protocol/amendments, and accuracy and completeness of records. The monitors will inspect sites' regulatory files to ensure that local regulatory requirements, in addition to U.S. Federal regulations, are being followed. They will also inspect sites' pharmacies to review product storage and management.

The site investigator will make study documents (e.g. consent forms, drug distribution forms, eCRFs) and pertinent hospital or clinic records readily available for inspection by the local IRB and the Harvard T.H. Chan School of Public Health IRB, the Botswana Ministry of Health, the site monitors, the FDA, the NIAID, the OHRP, and other local, U.S. or international regulatory entities for confirmation of the study data.

13. HUMAN SUBJECTS PROTECTIONS

Human subjects will be enrolled in this study. HIV-infected children who are study eligible will represent the population enrolled in this study. The health status of HIV-infected children participating in this study is expected to reflect that of optimally-treated HIV-infected children in Botswana. HIV-infected pediatric participants will receive the standard-of-care in accordance with Botswana National HIV treatment guidelines for at least 8 weeks from the date of bNAb treatment initiation, in addition to the bNAb intervention. Study participants will then undergo ART treatment interruption in Step 2 and will continue ongoing VRC01LS and 10-1074 infusions with close monitoring for up to 24 weeks. If viral load rebounds, ART will immediately be re-started. If there is no viral rebound, ART will be restarted after the final VRC01LS and 10-1074 infusions of the Step 2 Week 24 Visit (at Week 0 of Step 3).

Inclusion criteria for this study make it likely that only children with very low viral reservoir will undergo the dual bNAb intervention. All children will have started ART within the EIT study, with the majority from the antenatal cohort and having started <7 days of life, and all required to have maintained viral suppression <40 copies/mL for 24 weeks prior to enrollment.

